8.2.3 Duration of response

It is defined as the time from induction therapy response documentation and progression or relapse of lymphoma.

8.3 Safety endpoints

8.3.1 Grade 3-4 NCI-CTC AEs

All NCI-CTCAE grade 3-4 will be recorded.

8.4 Efficacy analysis

Efficacy analyses will be performed on the intention-to-treat population that includes all subjects enrolled. Response rate during and after lenalidomide treatment will be provided. Analyses will be performed to characterize PFS, TTP and OS. The Kaplan-Meier procedure will be used to characterize the time-to-event curves in the analyses where there is censoring. Otherwise, summary statistics (mean, standard deviation, median, minimum and maximum) will be provided. Parameters known to be potentially predictive of disease aggressiveness and

OSPEDALE SAN RAFFAELE
ISTITUTO DI RICOVERO E CURA A CARATTERE SCIENTIFICO

likelihood of response to lenalidomide in relapsed or refractory DLBCLs (tumour burden, LDH levels, time from last rituximab, etc) as well as prognostic subtypes (namely “germinal-center B cell type” – GBC - and “activated B-cell type” – ABC) or specific gene expression patterns/genetic signatures amenable to DLBCL subtypes - where available - will be taken into consideration in post-hoc multivariate efficacy analysis.

8.5 Safety analysis

All subjects who receive at least one week of study drug medication will be included in safety analysis. AEs, vital signs measurements, clinical laboratory information and concomitant medications will be tabulated and summarized. Subject incidence rates of all AEs and events requiring the discontinuation of study drug will be tabulated by system class, preferred term, and severity using MedDRA terms and NCI-CTCAE Version 3.0 severity grades. Time to first dose reduction will be summarized for each regimen. Death and clinically important AEs (including tumour lysis and thrombosis) will also be summarized.

All other measurements will be summarized using means, standard deviations, medians, minimum and maximum. Graphical display will be provided where useful in the interpretation of results.

9 Data handling and record keeping

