2.2 Secondary objectives

- To evaluate the safety of Lenalidomide maintenance therapy in this setting.
- To explore the efficacy of lenalidomide in the different DLBCL prognostic subtypes (see item 6.1.3)
- To investigate, when possible, whether the classification of DLBCL subtypes and the expression of specific candidate genes can provide prognostic information about the efficacy of lenalidomide in DLBCL subtype's

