2.4 Secondary endpoints

- Overall survival (OS), response rate (RR), adverse events (AE) and serious adverse events (SAE) rate

3 Overall study design

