If an adverse event considered associated with the study medication results in a patient's death, then the event will be listed as a "treatment-related mortality".

Procedures

All Adverse Events

All AEs, with the exception of progression of systemic AL-amyloidosis, that occur between the first study-related procedures and for 30 days following the last dose of investigational product will be reported. Resolution information after 30 days should also be provided for grade 3 to 4 drug related events. This subset should be followed up until resolution to a grade 1 or better.

Adverse events occurring after 30 days should also be reported if considered related to investigational product.

Clinically relevant changes in laboratory values must be recorded in the adverse event section of the CRF.

All AEs, regardless of seriousness, severity, or presumed relationship to study therapy, must be recorded in the source document and the CRF. Investigators must record in the CRF their opinion concerning the relationship of the adverse event to the study therapy. All measures required for adverse event management must be recorded in the source document.

The Principal Investigator assumes responsibility for appropriate reporting of adverse events to the regulatory authorities. The Principal Investigator must report these events to the appropriate Institutional Review Board (IRB) that approved the protocol unless otherwise required and documented by the IRB.

Serious Adverse Event (SAE) Reporting Report of Adverse Events to Regulatory Authorities and the Ethics Committee

The sponsor will inform relevant Regulatory Authorities and the Ethics Committee:

- of all relevant information about serious unexpected adverse events suspected to be related to the study medication that are fatal or life threatening as soon as possible, and in any case no later than seven days after knowledge of such a case. Relevant follow-up information for these cases will subsequently be submitted within an additional eight days.
- of all other serious unexpected events suspected to be related to the study medication as soon as possible, but within a maximum of fifteen days of first knowledge by the investigator.

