6.2.1.2 Immediate reporting by Investigator to Sponsor and Celgene

The investigator will inform the sponsor and Celgene of any serious adverse event. This applies to all SAEs, regardless of relationship to the study medication, that occur during the study, those made known to the Investigator(s) within 30 days after a subject's last dose of study drug, and those made known to the investigator(s) at any time that are suspected of being related to the study medication. This must be documented on an SAE form. This form must be completed in English and supplied to Celgene Europe Drug Safety within 24 hours/1 business day or at the latest on the following working day. The initial report must be as complete as possible, including details of the current illness and serious adverse event, and an assessment of the causal relationship between the event and the investigational product(s). Information not available at the time of the initial report (e.g., an end date for the adverse event or laboratory values received after the report) must be documented on a follow-up SAE form.

All adverse event reports must include the patient number, age, sex, weight, severity of reaction, relationship to study drug, date and time of administration of test medications and all concomitant medications, and medical treatment provided.

Safety Contact Information

	Safety Phone Number	Safety Fax/e-mail
Fondazione S. Raffaele Safety Desk	[contact]	[contact] [contact]
Celgene International Sarl Att. Drug Safety Department [name] 2017 Boudry CH-NE 24-H Emergency Contact Call Centre Direct [contact] and follow the instructions in the recorded message	[contact]	[contact] [contact]
Celgene S.r.l. [name] [name]	[name] [name]	[contact] [contact]

Sponsor Reporting to Celgene

The sponsor will provide Celgene with a copy of the annual safety report at the time of the submission to the regulatory authority and the Ethics Committee.

Pregnancies

Pregnancies occurring while subjects are on study drug or within 4 weeks after a subject's last dose of study drug are considered events to be reported immediately to Celgene. If the subject is on study drug the study drug is to be discontinued immediately and the subject is to be

OSPEDALE SAN RAFFAELE
ISTITUTO DI RICOVERO E CURA A CARATTERE SCIENTIFICO

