6.5.2 Initial examinations

- Informed consent
- Medical history
- Concomitant medications
- Vital signs (pulse, blood pressure, weight and height)
- Physical examination including ECOG Performance Status
- CBC
- Biochemistry: creatinine, uricemia, AST, ALT, GGT, ALP, total and direct bilirubin, LDH, beta2-microglobulin, Nat, Kal, Ca
- HIV, HCV, HBV testing
- Pregnancy test (for FCBP only)

6.5.3 Interim examinations (every week for the first 8 weeks, then every 2 weeks)

- Concomitant medications
- Vital signs (pulse, blood pressure, weight and height)
- Physical examination including ECOG Performance Status
- CBC

OSPEDALE SAN RAFFAELE
ISTITUTO DI RICOVERO E CURA A CARATTERE SCIENTIFICO

- Biochemistry
- Disease status evaluation (contrasted total body CT scan every 4 months)
- AE reports

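### The safety set in section 8.5 requires a week of lenalidomide, so patients who stop for toxicity or die sooner drop out of the safety tables

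*Combined protocol and SAP*

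**What the plan says.** Safety is a stated secondary objective in section 2.2 ("To evaluate the safety of Lenalidomide maintenance therapy in this setting"), and section 2.4 makes the "adverse events (AE) and serious adverse events (SAE) rate" a secondary endpoint.

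Section 8.5 defines the population for these analyses: "All subjects who receive at least one week of study drug medication will be included in safety analysis". It then lists the outputs, among them "Subject incidence rates of all AEs and events requiring the discontinuation of study drug will be tabulated" by system class, preferred term and severity, and a summary of deaths and clinically important events. No other safety population is defined, and no separate table or listing is planned for patients with less than a week of drug.

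No comparable exposure threshold appears elsewhere:

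- **Adverse event reporting (6.2.1.1):** events "that occur between the first study-related procedures and for 30 days following the last dose of investigational product will be reported".
- **Serious adverse events (6.2.1.2):** "This applies to all SAEs, regardless of relationship to the study medication, that occur during the study".
- **Efficacy (8.4):** "Efficacy analyses will be performed on the intention-to-treat population that includes all subjects enrolled".
- **End of participation (4.3.1):** stopping the drug for toxicity is a foreseen reason, with no minimum time on treatment.

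**The concern.** Entry to the safety set depends on something that happens after treatment starts and that toxicity can itself cause. A patient whose reaction ends treatment for good on day 4 has exactly the event that the discontinuation table is meant to count, and because of that event is removed from the table. The rule thus selects on the outcome being tabulated.

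The loss is narrower than all first-week toxicity. A patient who reacts on days 1 to 6 but continues, or interrupts and later accumulates a week of drug, stays in the set. Those lost are the patients who never reach a week.

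At stake is the accuracy of the planned summary of adverse event, discontinuation and death rates. This is a single-arm trial of at most 47 patients with no control group, so these tables are its main statement on tolerability. The rule can remove from them the earliest events severe enough to end treatment.

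**Working it through.** Section 8.5 states no rate, so there is no figure to reproduce. The check has two parts: how the definition works, and how far it can move a rate.

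**Definition.** Seven days of dosing and a week on treatment are both possible readings of the threshold. Under either, a patient who permanently stops or dies sooner is outside the set. Sections 6.2.1.1 and 6.2.1.2 ensure that the events are collected, but neither defines the population for the 8.5 tables.

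**Inputs for the size**

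- n = 47, the planned enrolment (sections 3.1 and 8.1). Assumption: all 47 receive at least one dose.
- k = number of patients who stop or die before a week of drug. The documents do not give it. Assumption: k = 1 or 2.
- Five later patients in the retained set have the event of interest, here discontinuation for toxicity. Assumption, for illustration only; zero is also shown.

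**Formula**

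Shift = rate in the 8.5 set - rate in all dosed patients = (k/47) × (rate in retained patients - rate in excluded patients).

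The sign depends only on whether the excluded patients had the event more or less often than the retained ones.

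**Results**

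| Early stops (k) | Had the event? | Later events | All dosed | 8.5 set | Shift (points) |
|---|---|---|---|---|---|
| 1 | yes | 0 | 1/47 = 2.1% | 0/46 = 0.0% | -2.1 |
| 1 | yes | 5 | 6/47 = 12.8% | 5/46 = 10.9% | -1.9 |
| 2 | yes | 5 | 7/47 = 14.9% | 5/45 = 11.1% | -3.8 |
| 1 | no | 5 | 5/47 = 10.6% | 5/46 = 10.9% | +0.2 |
| 2 | no | 5 | 5/47 = 10.6% | 5/45 = 11.1% | +0.5 |

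Check of the second row by the formula: (1/47) × (5/46 - 1) = 0.0213 × (-0.891) = -0.019, or -1.9 points.

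The effect is asymmetric. In these examples an early toxic stop moves the rate about eight times as far as an event-free one (1.9 against 0.2, and 3.8 against 0.5). The largest shift that one patient can cause is 1/47 = 2.1 points, when no retained patient has the event. That row also describes a sole early toxic death, which would read as no deaths among 46 patients in the 8.5 summary.

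**The case against.** The strongest case against is that the consequence is small, conditional and confined to descriptive tables.

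- **Size is assumed.** The documents give no first-week stopping rate, and it could be zero. This stands.
- **Few patients are likely to qualify.** Section 6.5.3 schedules examinations, with blood counts and biochemistry, "every week for the first 8 weeks, then every 2 weeks". The first check falls at about one week of drug, so a stop prompted by a laboratory finding there may already meet the threshold. What remains is mainly symptomatic permanent stops and deaths in the first days. This stands as a limit on size.
- **The shifts are small against the trial's precision.** Exact 95% intervals are 4.8% to 25.7% for 6/47 and 3.6% to 23.6% for 5/46; for 7/47 and 5/45 they are 6.2% to 28.3% and 3.7% to 24.1%. The shift lies well inside them. That is correct, but the intervals describe sampling error and do not excuse a systematic omission that is easily avoided.
- **The events are not lost to oversight.** Section 8.3.1 has all grade 3-4 events recorded, section 4.3.2 has the reason for every termination entered in the CRF, section 6.2.2 gives the IDMC ongoing safety data, section 6.2.1.1 lists treatment-related deaths, and overall survival (8.2.1) counts death from any cause. All true, but none of these supplies or corrects the 8.5 incidence rates.
- **The wording is not explicitly exclusive.** Section 8.5 says who is included and does not add that nobody else is. Even so, it is the only population given for the tables that follow, and a programmer would take it as the denominator.
- **Direction is not fixed.** Section 4.3.2 also lists withdrawn consent and poor compliance as reasons for leaving, and event-free early stops push the rate up slightly. The downward bias is therefore claimed only where early stops are due to toxicity.
- **No decision depends on these rates.** There is no safety hypothesis or toxicity stopping boundary on this set, and the two-stage rule in 8.1 uses progression-free status. This stands, and it keeps the point well below the primary analysis in importance.

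**Conclusion.** The concern holds. As written, section 8.5 leaves patients with less than a week of lenalidomide out of its adverse event, discontinuation and death summaries, and nothing else in the document repairs those rates. Where the early stop is due to toxicity, the reported rate is biased low by up to 2.1 points per such patient if no retained patient has the event; in the worked examples with five later events the bias is 1.9 points for one patient and 3.8 for two. Where early stoppers are event-free, the rate is 0.2 or 0.5 points too high.

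The reading of the definition is firm. The sizes rest on assumed counts and on all 47 patients being dosed, and the true effect may be small or nil. The primary endpoint and its decision rule are unaffected. The point should be corrected, but it does not threaten the trial's main conclusion.

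**What to change.** In section 8.5, replace the one-week exposure condition with receipt of at least one dose of study drug, and leave the rest of the section as it is.

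The cost is one phrase. No new data, visits or patients are needed, because section 6.2.1.1 already requires these events to be recorded, and treatment and the two-stage design do not change. Reported toxicity may come out slightly higher. The new definition cannot drop a dosed patient, so the tables no longer depend on why patients stopped early.

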9.1 Definition of source documents and data

All parameters asked for in the case report form (CRF) should be documented in the source documents.

Parameter	Source document
Medical history / patient's eligibility	- patients' charts
Therapy	- patients' charts
Disease status	- patients' charts - histological / radiological / laboratory reports
Adverse events	- patients' charts - laboratory reports - medical reports - nurses documentation

OSPEDALE SAN RAFFAELE
ISTITUTO DI RICOVERO E CURA A CARATTERE SCIENTIFICO

Physical examination	- patients' charts
Disease response	- patients' charts
	- histological / radiological / laboratory reports
Survival	- patients' charts, autopsy report if available

For the following parameter, the CRF might be used as source document:

- ECOG Performance Status

9.2 Patient registration

Registration of patients will be performed by responsible investigator of every participating center by sending a fulfilled Registration Form at the attention of the Principal Investigator by fax at **[contact]**.

9.3 Documentation of data in the case report form (CRF)

All relevant data collected during the study for all of the patients enrolled in the study shall be entered in the CRF by the responsible investigator or someone authorised by him in a timely manner so that they are clear and legible. The physician shall confirm the completeness, correctness and plausibility of the data by his signature with the date. The entries shall be made with black ball-point pen.

The properly filled in CRF will remain in the trial centre.

9.4 Data management

The data will be recorded in the CRF designed for this study. All CRF will be checked for completeness, plausibility and compliance with the ICH guidelines and the institutional SOPs.

9.5 Record keeping

The investigator shall arrange for the retention of the patient identification list, the signed informed consent forms and the signed data protection declaration for at least 15 years after the completion or discontinuation of the study. Patient files and other source data shall be kept for the maximum period of time permitted by the hospital.

The sponsor will keep essential documents according to ICH-GCP.

10. Study drug material and management

10.1 Supplier(s)

- Celgene Corporation will supply lenalidomide.

10.2 Dosage form

- Lenalidomide will be supplied as 5mg, 10mg and 25mg capsules for oral administration.

10.3 Packaging

- Lenalidomide will be shipped to the pharmacy at the study site in individual bottles each containing 21 capsules of lenalidomide 5mg, 10mg or 25mg.
 - Patients will be treated for 24 cycles of therapy, unless treatment is discontinued earlier due to disease progression or unacceptable toxicity. At each cycle, patients will be provided with a number of bottles containing lenalidomide 5, 10 or 25mg sufficient to cover 21 days of treatment.

10.4 Special Handling Instructions

Women of childbearing potential should not handle or administer the clinical dosage forms unless they are wearing gloves.

10.5 Labelling

The label for study drug supplied by Celgene will detail Sponsor's name and address, the protocol number, EudraCT number, product name, dosage form, and strength, medication identification/kit number, dosing instructions, storage conditions, the quantity of study drug contained, and required caution statements and/or regulatory statements as applicable. Additional information may be included on the label as needed and/or applicable.

10.6 Receipt of study drug

The Investigator is responsible for taking an inventory of each shipment of study drug received, and comparing it with the accompanying study drug accountability form. The Investigator will verify the accuracy of the information on the form, sign and date it, retain a copy in the study file, and return a copy to Celgene or its representative.

10.7 Storage

Lenalidomide should be stored at room temperature away from direct sunlight and protected from excessive heat and cold.

At the study site, all investigational study drugs will be stored in a double locked, safe area to prevent unauthorized access.

10.8 Unused study drug supplies

Patients will be instructed to return empty bottles or unused capsules. Unused or returned study drug will be destroyed locally in compliance with local pharmacy destruction procedures and drug disposition must be appropriately documented in the study file. If any study drug is lost or damaged, its disposition should be documented in the source documents.

10.9 Record of administration

Accurate records will be kept of all study drug administration (including dispensing and dosing) in the study record files.

11 Formalities / regulatory aspects

11.1 Legal regulations and guidelines

This study will be conducted in conformance with the regulations of the latest versions of the applicable laws, the “Declaration of Helsinki” and the principles of good clinical practice (ICH-GCP).

11.2 Patient insurance

In accordance with the drug regulations, all patients participating in the study have been insured for injury or death.

